8.3.3 DEFINITION OF SERIOUS ADVERSE EVENTS (SAE)

Serious Adverse Event

A serious adverse event (SAE) is an adverse event occurring at any dose that results in any of the following outcomes or actions:

- results in death
- is a life-threatening adverse event (i.e., the patient was at risk of death at the time of the event); it does not refer to an event which hypothetically might have caused death if it were more severe
- requires inpatient hospitalization or prolongation of existing hospitalization, which means that hospital inpatient admission or prolongation of hospital stay were required for treatment of an adverse event, or that they occurred as a consequence of the event

Hospitalizations scheduled before the patient signed the ICF will not be considered serious adverse events, unless there was worsening of the pre-existing condition during the patient's participation in this study.
- results in persistent or significant disability/incapacity (refers to a substantial disruption of one's ability to conduct normal life functions)
- is a congenital anomaly/birth defect
- an important medical event that may not result in death, be life-threatening, or require hospitalization, but may jeopardize the patient and may require medical intervention to prevent 1 of the outcomes listed in this definition

Examples of such events are intensive treatment in an emergency room or at home for allergic bronchospasm; blood dyscrasias or convulsions that do not result in hospitalization; or the development of drug dependency or drug abuse. Note: Any suspected transmission of an infectious agent via a medicinal product is considered an important medical event.

All occurrences of possible drug-induced liver injury that meet Hy's law criteria, defined as **all** of the below, must be reported by the investigator to the sponsor as a serious adverse event:

- alanine aminotransferase or aspartate aminotransferase increase of >3x the upper limit of normal (ULN)
- total bilirubin increase of >2x ULN

- absence of initial findings of cholestasis (i.e., no substantial increase of alkaline phosphatase)

An adverse event that does not meet any of the criteria for seriousness listed above will be regarded as a non-serious adverse event.

8.3.4 SERIOUS ADVERSE EVENT REPORTING

In keeping with good clinical practice or good pharmacovigilance practice, and 21 C.F.R. Part 314 as the case may be, the external sponsor/collaborator will be required to report and notify the FDA, Institutional Review Boards (IRBs), Teva Pharmaceuticals (Teva), and any other collaborators/investigators of all situations mentioned below, within twenty-four (24) hours from receiving information of the situation. The event will be reported to Teva by submitting the collected information to the Teva Local Safety Officer.

- (a) All related Serious Adverse Events
- (b) All Serious Adverse Device Effects
- (c) Any medical event which may reasonably be believed to impair the integrity, validity or ongoing viability of the Study

Adverse Event. Sponsor/collaborator acknowledges that Company is required to comply fully and promptly with all regulatory safety reporting requirements regarding its products. The investigator being the sponsor of the study has sole responsibility for reporting of adverse events to the FDA, IRBs and/or investigators. For informational purposes any correspondence to the FDA regarding adverse events or other safety issues will be simultaneously copied to the Company via email ([contact]) or [contact]). The Investigator will communicate the occurrence of any serious adverse events which he or she believes to be definitely, likely, possibly or probably related to the Study Product, and any exposure of a pregnant study participant to the Study Product, within 24 hours of becoming aware of the event. In the case of non-interventional studies, the Investigator also will communicate all related, non-serious adverse events to Company within 24 hours of becoming aware of the event. Please note that the reporting period begins when a patient signs the informed consent, and ends 30 days after the discontinuation of dosing or completion of the patient's participation in the Study if the last scheduled visit occurs at a later time. In addition, the Investigator must notify Company of any serious adverse events that may occur after this time period which he or she believes to be definitely, likely, possibly or probably related to the Study Product.

The MedWatch 3500A form should be utilized to report serious adverse events to the FDA.

A serious adverse event or reaction is any untoward medical occurrence that at any dose:

- Results in death;
- Is life-threatening (meaning that the patient was at immediate risk of death as the event occurred, but not including events that could cause death if they occurred in a more severe form);
- Requires inpatient hospitalization or prolongation of existing hospitalization;
- Results in a persistent or significant disability/incapacity;
- Is a congenital anomaly or birth defect;

- Results in the development of drug dependency or drug abuse;
- An important medical event that may not result in death, be life threatening, or require hospitalization, but may jeopardize the patient and require medical intervention to prevent one of the outcomes listed above.

For the purpose of this Agreement, these terms shall have the same meaning as the terms used in the provisions of the Code of Federal Regulations governing drug and biologic safety reporting. See 21 CFR 314.80(a); 600.80(a). Additionally, pregnancy exposure and any safety information as reasonably requested by Company, will also be deemed to be adverse events for purposes of this Agreement. Investigator shall use his/her judgment to determine the relationship between the serious adverse event and the Study Product. In the event the IRB requests additional safety information from Investigator, Investigator shall notify Company of such request within one (1) business day.

Investigator and Institution further agree to report all Adverse Events in compliance with all applicable legal and regulatory requirements, and in accordance with any requirements provided by Company.

8.3.5 REPORTING EVENTS TO PARTICIPANTS

Events that involve device failure that will affect drug delivery as noted by the sponsor or any other new safety requirements that may be required by the FDA will be reported to participants.

8.3.6 EVENTS OF SPECIAL INTEREST

There are no events of special interest anticipated in this study.

9 STATISTICAL CONSIDERATIONS

9.1 STATISTICAL HYPOTHESES

- Primary Efficacy Endpoint(s): Establish group-level daily/weekly baseline normative values for: (1) mean and median number of doses of ProAir® Digihaler™ and AirDuo® Digihaler™, and per-inhalation baseline normative values for (2) peak inspiratory flow (PIF), (3) inspiratory time and (4) volume. We will test the hypothesis that patient-specific baseline usage values are significantly different from usage values collected during or leading up to exacerbation events.
- Secondary Efficacy Endpoint(s): 1. Test the hypothesis that imminent exacerbation events can be predicted using Digihaler™ inhalation parameter measurements. 2. Test the hypothesis that PIF is linearly (or non-linearly) related to FVC and FEV1. Test the hypothesis that there exists a threshold for change in PIF that is associated with a clinically meaningful change (>10%) in lung function. 3. Test the hypothesis that patients with low, moderate, and high adherence to maintenance inhalers have significantly different asthma outcomes. 4. Test the hypothesis that non-responders, partial, and complete responders have significantly different Digihaler™ inhalation parameters. 5. Test the hypothesis that future response to biologics can be predicted using clinical, biological, and digital (inhalation) markers.

9.2 SAMPLE SIZE DETERMINATION

Sample size calculations were based on peak inspiratory flow measurements.

Based on population-based estimates of peak inspiratory flow:

<https://www.ncbi.nlm.nih.gov/pmc/articles/PMC5328129/> The mean was 115 and standard deviation was 15. With a 100-patient sample, 95% CI of our estimate of the mean would be plus or minus 3, e.g. 115 (95 CI 112 – 118).

The machine learning model will be performed based on the most common measure to evaluate performance which is discrimination that is assessed by an AUROC. If we have a 100-patient sample and assume a 50% event rate (<http://www.biosoft.hacettepe.edu.tr/easyROC>), we would have adequate power to conclude that a model with an AUROC performance of > 0.65 has confidence intervals that won't cross 0.5 (which would be a model that is no better than chance).

9.3 POPULATIONS FOR ANALYSES

University of Michigan patients currently receiving biologics or with a pending approval for biologics for asthma.

9.4 STATISTICAL ANALYSES

9.4.1 GENERAL APPROACH

We will perform a retrospective analysis of prospectively enrolled patient data. Following completion of the study's data collection period, data from the Digihaler™ asthma inhalers will be downloaded to secure servers, joined to clinical data from the electronic medical record (including exacerbation event data) and patient questionnaire responses, and analyzed using R statistical analysis software. The University of Michigan Morphomics Analysis Group will collaborate with the TEVA analytics team to produce a rigorous and reproducible research result. An alpha level of 0.05 will be used to determine "statistical significance" with a Bonferroni correction ($\alpha / \# \text{ tests}$) applied to account for multiple testing when appropriate.

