9.4.3 ANALYSIS OF THE SECONDARY ENDPOINT(S)

1. To develop an algorithm that can identify probable imminent exacerbation events using Digihaler™ inhalation parameter measurements, we will compare the performance of several different machine learning regression models. Since we expect our training set to be relatively small with a low event rate, we plan to use the entire inhalation parameter dataset for model training but will employ repeated k-fold cross-validation to reduce variance (over-fitting) and include non-linear features to reduce bias (under-fitting). Examples of features that could be computed and included in this model include but are not limited to: difference between current value and patient-specific 7-day moving average, difference between current value and patient-specific 24-hour moving average, 7-day sample entropy, 24-hour sample entropy, difference in Min-Max over last 24 hours, etc.

A logistic regression model would treat the outcome (exacerbation) as a binary (Yes/No) event. The output of this model would be a daily probability between 0 and 1 that an exacerbation event will occur within a certain period of time. Different models will be fit for different periods of time (e.g., 24, 48, 72 hours) and the performance of each model assessed and compared to others. A recurrent event survival model would treat the exacerbations as discrete events in time. The output of this model would be the predicted time (e.g., in decimal days or hours) until the next event. Other models may include convolutional and/or recurrent neural networks (RNN) with LSTM or GRU architecture with varied numbers of hidden layers.

2. To determine whether and how PIF is associated with FEV1 and FVC, we assess the linearity and strength of the relationship using scatter plots, calculate the paired correlations (Pearson, Kendall, and Spearman), and compute univariate linear regression equations with PIF as the predictor and FEV1 or

FVC as the response. If non-linearity is found, we will determine the appropriate PIF transformation or polynomial term to use in the regression. Regression summary statistics (e.g., R-squared, Mean Absolute Error, Coefficients, and p-values) will be reported.

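### Bonferroni in 9.4.1 is valid but dominated by Holm, and 9.4.3 item 2 does not name the inferential PIF test, so the divisor can be read as 2 or 8

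*Combined protocol and SAP*

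**What the plan says.** Section 9.4.1 of the combined protocol and SAP states: "An alpha level of 0.05 will be used to determine" significance, "with a Bonferroni correction" that divides alpha by the number of tests, "applied to account for multiple testing when appropriate". It does not list the tests or define the family.

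Section 9.1, secondary hypothesis 2, reads: "Test the hypothesis that PIF is linearly (or non-linearly) related to FVC and FEV1". That is one hypothesis for each of two outcomes. To address it, 9.4.3 item 2 will "calculate the paired correlations (Pearson, Kendall, and Spearman), and compute univariate linear regression equations" with FEV1 or FVC as the response. It then says: "Regression summary statistics (e.g., R-squared, Mean Absolute Error, Coefficients, and p-values) will be reported". A transformation or polynomial term for PIF is allowed if the relation proves non-linear. In the Section 3 table, the correlation coefficients and the regression statistics appear together under a label that calls them tests.

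The set of secondary hypotheses differs by section:

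- Section 1.1 has four secondary objectives, Section 3 has three, and 9.1 has five secondary hypotheses.
- Exacerbation prediction is secondary in 1.1 and 9.1 but exploratory in Section 3.
- Responder prediction is exploratory in 1.1 and 3, but 9.1 lists it as a secondary hypothesis: "Test the hypothesis that future response to biologics can be predicted using clinical, biological, and digital (inhalation) markers".
- Categorical response appears in Section 3 under both secondary and exploratory.

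**The concern.** Two things can be improved.

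First, once a list of tests is fixed, Bonferroni has no advantage over Holm in error control. Any power that it gives up is given up for nothing.

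Second, a rule that divides alpha by the number of tests needs that number, and the plan does not supply it. For the PIF question alone a reasonable analyst could count two tests or eight. If eight are counted, the Pearson test and the slope test are charged separately although they are the same test while PIF enters linearly. With 100 patients, the choice between 0.00625 and 0.025 can decide whether a moderate PIF association is declared, and the choice could be made after the data are seen.

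**Working it through.** **Inputs from the documents.** Alpha 0.05 (9.4.1); 100 patients, PIF mean 115 and SD 15 (9.2); two outcomes and four listed analyses per outcome (9.4.3 item 2).

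**Assumptions, because the documents are silent.** Two-sided tests; one PIF–outcome pair per patient; no dropout; normal data; true correlation r from 0.20 to 0.35, with 0.50 as an upper check; correlation 0.8 between FEV1 and FVC in the simulations.

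**1. The plan's own figures.** The half-width for mean PIF is 1.96 × 15/√100 = 2.94, which agrees with the stated plus or minus 3. For an AUROC of 0.65 with 50 events and 50 non-events, the Hanley–McNeil standard error is 0.0548. The interval is 0.65 ± 1.96 × 0.0548 = 0.543 to 0.757, which excludes 0.5 as stated. Neither figure involves the multiplicity correction. The plan gives no adjusted alpha or power for the PIF tests.

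**2. Holm against Bonferroni.** With m tests, Bonferroni compares every p-value with α/m. Holm compares the ordered p-values with α/m, α/(m−1), …, α and stops at the first failure. No Holm threshold is below α/m, so every Bonferroni rejection is also a Holm rejection. Both rest on the same union bound and need no independence.

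**3. The duplicate test.** The Pearson statistic r√(n−2)/√(1−r²) equals the slope divided by its standard error, with n−2 degrees of freedom. In 1,000 simulated datasets the two p-values differed by at most 1e-15. The 4 × 2 = 8 analyses therefore contain at most 6 distinct tests. The identity fails if PIF is transformed or given a polynomial term.

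**4. Thresholds.** Counting eight: 0.05/8 = 0.00625. Counting two: 0.05/2 = 0.025. Holm on two: 0.025, then 0.05.

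**5. Power per outcome.** By Fisher's z, power = Φ(atanh(r)√97 − z at 1−α/2). At r = 0.30, atanh(0.30)√97 = 3.048:

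- α = 0.00625: Φ(3.048 − 2.734) = 0.623
- α = 0.025: Φ(3.048 − 2.241) = 0.790
- α = 0.05: Φ(3.048 − 1.960) = 0.862

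Holm on two tests must lie between the last two values. The last column and the bracketed values are simulated (3,000 runs, both outcomes related).

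| True r | Unadjusted | Bonferroni, 8 | Bonferroni, 2 | Holm, 2 |
|---|---|---|---|---|
| 0.20 | 0.515 | 0.230 (0.24) | 0.403 | 0.45 |
| 0.25 | 0.711 | 0.413 (0.42) | 0.608 | 0.66 |
| 0.30 | 0.862 | 0.623 (0.62) | 0.790 | 0.83 |
| 0.35 | 0.949 | 0.806 (0.81) | 0.913 | 0.94 |
| 0.50 | 1.000 | 0.996 | 0.999 | between 0.999 and 1.000 |

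If only FEV1 is related (r = 0.30), simulated power is 0.63 with Bonferroni over eight, and 0.80 with either Bonferroni or Holm over two.

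**6. Where the gain comes from.** At r = 0.30 the rise from 0.62 to 0.83 is 21 points. About 17 come from reducing eight tests to two (0.62 to 0.79) and about 4 from Holm (0.79 to 0.83).

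**7. Family-wise error.** In 6,000 null runs it was 0.040 for Holm on two tests. Bonferroni over eight gave 0.011 if only the Pearson/slope test counts and 0.015 if any of the four counts.

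**The case against.** The strongest reply is that the plan never says eight tests are counted. Section 9.4.3 item 2 names p-values only for the regression; the correlations are to be calculated, which reads as description. On that reading there are two p-values, the threshold is already 0.025, and Holm adds little. This stands: the contrast of 0.62 with 0.83 is the worst-case count and not the plan's established behaviour. What survives is that Section 3 labels the correlations as tests and that no section names the inferential one.

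Three stronger readings are tempting, and the documents do not support them.

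- A reader might infer that the plan as written throws away about 20 points of power, and that Holm recovers them. The count of eight is not stated, and most of that gain comes from using one test per outcome. If success meant any of the four analyses reaching 0.00625, power at r = 0.30 would be 0.64 to 0.65, which narrows the gap slightly.
- A reader might infer from the discretion in 9.4.1 that the tests will go uncorrected and the error rate will be inflated. Any of the eight analyses at an unadjusted 0.05 would give a null rate of 0.103 in the same simulation, but nothing says the analyses will be used that way.
- A reader might treat the five secondary hypotheses in 9.1 as five independent tests and work out an average power loss. Hypotheses 1 and 5 concern prediction models, to be judged by AUROC (4.2, 9.2) and cross-validation (9.4.3). Hypotheses 3 and 4 each contain several outcomes or parameters. That family is not the plan's.

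It is also fair that Bonferroni is a legitimate conservative choice, that Section 8.1 disclaims any evaluation of drug efficacy, and that the sample size does not depend on this correction.

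**Conclusion.** The point holds as a free improvement of low severity, to be considered. Replacing Bonferroni with Holm cannot lose a rejection or weaken family-wise control on a given list. The list itself needs to be written down, because Holm needs an enumerated family just as Bonferroni does.

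The size depends on the count. Under the eight-analysis reading the gain is 13 to 24 points per outcome for r between 0.20 and 0.35, when both outcomes are related. Under the two-test reading it is about 0 to 5 points, and nil if only one outcome is related. At r = 0.50 it is immaterial on either reading. Section 3 says that little is known about the PIF–FEV1 correlation, so no single value of r should be relied on.

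All power figures assume one pair per patient. Home spirometry is requested at least three days a week (8.1.2.5) and PIF is recorded at each inhalation, but the unit of analysis is not stated. Treating repeated pairs as independent would undermine the p-values under any correction; that is a separate matter.

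**What to change.** - **9.4.1:** replace Bonferroni with Holm's step-down procedure over an explicit list of the tests that will yield p-values. State whether the comparison of baseline with exacerbation usage in 9.1, and each adherence outcome and inhalation parameter in 9.4.3 items 3 and 4, belongs to that list.
- **9.4.3 item 2:** name the PIF regression test as the single inferential test for each of FEV1 and FVC, and say what that test is if PIF is transformed or enters as a polynomial. Report Pearson, Kendall and Spearman as descriptive, and relabel them accordingly in the Section 3 table.
- **1.1, 3 and 9.1:** make the secondary hypotheses agree. Keep the prediction-model objectives, judged by AUROC, out of the p-value family.

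The cost is wording only; no patients, visits or data collection change. Holm does not give simple simultaneous confidence intervals, but the plan calls for none.

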9.4.2 ANALYSIS OF THE PRIMARY EFFICACY ENDPOINT(S)

To establish normative baseline values, summary statistics (mean, standard deviation, median, IQR) will be computed for the number of doses taken per individual, stratified by type of inhaler (maintenance, rescue), and aggregated per day and for particular times of day (morning, midday, afternoon, evening, overnight). Per-inhalation summary statistics will be computed for PIF, inspiratory time, and inspiratory volume. Inhalation data within +/- 14 days of an acute exacerbation event will be identified and excluded from normative baseline calculations.

9.4.3 ANALYSIS OF THE SECONDARY ENDPOINT(S)

1. To develop an algorithm that can identify probable imminent exacerbation events using Digihaler™ inhalation parameter measurements, we will compare the performance of several different machine learning regression models. Since we expect our training set to be relatively small with a low event rate, we plan to use the entire inhalation parameter dataset for model training but will employ repeated k-fold cross-validation to reduce variance (over-fitting) and include non-linear features to reduce bias (under-fitting). Examples of features that could be computed and included in this model include but are not limited to: difference between current value and patient-specific 7-day moving average, difference between current value and patient-specific 24-hour moving average, 7-day sample entropy, 24-hour sample entropy, difference in Min-Max over last 24 hours, etc.

A logistic regression model would treat the outcome (exacerbation) as a binary (Yes/No) event. The output of this model would be a daily probability between 0 and 1 that an exacerbation event will occur within a certain period of time. Different models will be fit for different periods of time (e.g., 24, 48, 72 hours) and the performance of each model assessed and compared to others. A recurrent event survival model would treat the exacerbations as discrete events in time. The output of this model would be the predicted time (e.g., in decimal days or hours) until the next event. Other models may include convolutional and/or recurrent neural networks (RNN) with LSTM or GRU architecture with varied numbers of hidden layers.

2. To determine whether and how PIF is associated with FEV1 and FVC, we assess the linearity and strength of the relationship using scatter plots, calculate the paired correlations (Pearson, Kendall, and Spearman), and compute univariate linear regression equations with PIF as the predictor and FEV1 or

FVC as the response. If non-linearity is found, we will determine the appropriate PIF transformation or polynomial term to use in the regression. Regression summary statistics (e.g., R-squared, Mean Absolute Error, Coefficients, and p-values) will be reported.

3. Patients will be assigned to one of three adherence groups (low, moderate, high) based on Digihaler™ inhalation usage parameters over the previous month. We will use the Chi-squared test to determine if group differences exist for each asthma outcome over the next month, and Tukey's Honest Significant Difference test to determine which groups are significantly different.

4. Patients will be assigned to one of three biologics response groups (non, partial, complete) based on six asthma factors (described earlier). We will use the Chi-squared test to determine if group differences exist for each inhalation parameter, and Tukey's Honest Significant Difference test to determine which groups are significantly different.

5. To develop an algorithm that can predict patients that will respond to biologics regression or classification models. Since we expect our training set to be relatively small with a low event rate, we plan to use the entire inhalation parameter dataset for model training but will employ repeated k-fold cross-validation to reduce variance (over-fitting) and include non-linear features to reduce bias (under-fitting). We do not know a priori whether regression or classification would be the appropriate approach to this question so we will test models using both approaches. The classification approach can be formulated as either a two-class problem – Non vs. Partial or Complete responders, or Non or Partial vs. Complete responders – or a three-class problem – Non vs. Partial vs. Complete. The regression approach requires a two-class formulation using logistic regression. Different models will be fit for different formulations and the performance of each model assessed and compared to others.

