8.1.2.3 ASTHMA EXACERBATIONS

During the study, an asthma exacerbation will be defined as a worsening of asthma symptoms (defined below) that leads to any of the following:

- Administration of a bolus/burst of systemic corticosteroids (one dose of IV or IM steroids or at least consecutive three days of oral corticosteroids).
- An emergency room or urgent care visit for asthma related symptoms that required oral/IV/IM corticosteroids.
- An inpatient hospitalization (defined as admission to an inpatient facility and/or evaluation and treatment in a healthcare facility for ≥ 24 hrs) due to asthma.

For the protocol, the start date of the exacerbation will be based on the day of ER, urgent care visits or hospitalization. For those that did not experience one of these events, the day of the first dose of OCS will be used as the initial day of the exacerbation. The last day of systemic corticosteroids will be used as an end date of the exacerbation. If less than 7 days has elapsed between the end of the first exacerbation and the beginning of new symptoms, then this will be considered a relapse of the initial episode rather than a new episode. Subjects that experience exacerbations post enrollment will be treated per standard of care by the patient's physician.

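### The exacerbation-prediction model has no at-risk rule; read literally, most days inside an episode or its relapse window are trained and scored as non-events

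*Combined protocol and SAP*

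**What the plan says.** Section 9.4.3 item 1 describes a logistic model whose output is "a daily probability between 0 and 1 that an exacerbation event will occur within a certain period of time", with separate fits for horizons such as 24, 48 and 72 hours. On outcome coding it says: "A logistic regression model would treat the outcome (exacerbation) as a binary (Yes/No) event". On the rows used it says "we plan to use the entire inhalation parameter dataset for model training", with repeated k-fold cross-validation. It also mentions a recurrent-event survival model. For neither model does it state an at-risk interval or a label for days when an exacerbation is already under way.

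Section 8.1.2.3 dates an exacerbation from the emergency, urgent-care or hospital day, or otherwise from the first oral steroid dose, to the last day of systemic steroids. If new symptoms begin under 7 days after that end, "then this will be considered a relapse of the initial episode rather than a new episode".

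Section 9.4.2 removes inhalation data within 14 days either side of an exacerbation, but these data are "excluded from normative baseline calculations"; nothing extends the removal to the prediction model. Section 9.1 hypothesises that usage both during and leading up to exacerbations differs from the patient's own baseline.

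**The concern.** A look-ahead model asks, on each day, whether a new event will start within the horizon. Where the event definition rules out a new start, the answer is No whatever the inhaler shows. By the plan's own hypothesis these are days on which readings are likely to look abnormal, much like the pre-event days the model has to detect. Kept as ordinary negatives, they teach the model that abnormal readings often precede nothing, and at evaluation they turn recognition of a sick patient into a false positive.

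Cross-validation does not expose this, because the test folds carry the same labels. The confusion matrix promised in section 1.1 (exploratory endpoint 11) and in the section 3 table would carry the distortion into the reported sensitivity, specificity and accuracy.

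**Working it through.** **The plan's own figures.** Section 9.2 reproduces. The half-width for mean peak inspiratory flow is 1.96 × 15/√100 = 2.94, or about ±3. For an AUROC of 0.65 with 50 events and 50 non-events, the Hanley-McNeil standard error is 0.055, so the 95% CI is 0.65 ± 1.96 × 0.055 = 0.543 to 0.757, which excludes 0.5. Both count patients, not patient-days, so neither bears on this point.

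**Day count.** Let day 0 be the start date, L the number of steroid days (course beginning on day 0) and H the horizon in days.
- The episode ends on day L−1.
- A gap under 7 days is a relapse, so the last blocked day is (L−1)+6 = L+5 and the earliest new event is on day L+6.
- Day d looks ahead to days d+1 to d+H. Its label must be zero if d+H ≤ L+5, that is d ≤ L+5−H.
- Days 0 to L+5−H are therefore forced zeros: L+6−H days.
- Positive days per event are those just before the start: at most H.

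The values L = 1 (one IV or IM dose) and L = 3 (shortest oral burst) come from 8.1.2.3; L = 10 is assumed.

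| Steroid days L | 24 h (H=1) | 48 h (H=2) | 72 h (H=3) |
|---|---|---|---|
| 1 | 6 vs 1 | 5 vs 2 | 4 vs 3 |
| 3 | 8 vs 1 | 7 vs 2 | 6 vs 3 |
| 10 (assumed) | 15 vs 1 | 14 vs 2 | 13 vs 3 |

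Forced zeros outnumber positives in every cell, from 4/3 = 1.3:1 to 15:1. The last H days of the window are not forced: an event on day L+6 makes them positive. In the other direction, the 7 days run to new symptoms while a start date is the care visit or first steroid dose, so the true no-start period can be longer than this count.

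**Effect on the model (illustration).** The documents give no event rate, course length or signal size, so these are assumptions. Simulated data: 100 patients × 336 days; one signal with unit-SD noise that rises before the event, stays at its peak through the steroid days and decays linearly over the next 7 days. Logistic regression was fitted on all days and on at-risk days only (forced zeros removed). PPV is taken above the cut giving 99% specificity among at-risk days.

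| Events/yr, L, horizon, peak | Slope: all vs at-risk | PPV: all vs at-risk | AUROC: all vs at-risk |
|---|---|---|---|
| 0.5, 3, 72 h, 2 SD | 0.93 vs 1.00 | 3.5% vs 4.3% | 0.749 vs 0.752 |
| 1, 5, 72 h, 2 SD | 0.84 vs 1.00 | 5.1% vs 8.2% | 0.745 vs 0.755 |
| 1, 5, 24 h, 2 SD | 1.19 vs 1.48 | 3.1% vs 5.1% | 0.845 vs 0.855 |
| 2, 10, 24 h, 2 SD | 0.94 vs 1.48 | 3.0% vs 9.5% | 0.825 vs 0.856 |
| 1, 5, 72 h, 1 SD | 0.48 vs 0.51 | 2.5% vs 2.9% | 0.635 vs 0.640 |
| 1, 5, 72 h, 3 SD | 0.94 vs 1.45 | 7.6% vs 16.4% | 0.824 vs 0.838 |

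Over 0.5 to 2 events per year, 3 to 10 steroid days and a 2 SD peak, forced zeros are only about 1 to 7.5% of non-event days but 18 to 68% of days above the cut. Keeping them lowers the slope by about 7 to 36%, PPV by roughly 20 to 70%, and AUROC by 0.003 to 0.03.

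**Feature choice matters.** A second illustration assumed 2 attacks a year, Poisson puff counts averaging 2 a day at baseline, 4 before and 6 during an attack, a 10-day burst and a 72-hour horizon. Using current value minus 7-day average (a feature item 1 lists), with a cut at 95% specificity, AUROC was 0.741 with all days and 0.746 without the window days; PPV was 7.2% and 9.3%. With raw use added to that feature, AUROC was 0.747 and 0.812.

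**The case against.** The strongest reply is that the plan never says these days are non-events. The sentence about the entire dataset opens with "Since we expect our training set to be relatively small with a low event rate" and is paired with cross-validation; its main sense is that no test set will be held out. Item 5 of the same section repeats it for the biologic-response model, where no relapse window exists. Coding in-episode days as ongoing events, dropping them, or treating them as not at risk in the recurrent-event model is not ruled out. This stands: the defect is an omission, and a reader who infers that the plan deliberately labels attack days as safe goes beyond the text. But the three codings give different models, section 9.4.1 promises a reproducible result, and the literal reading gives No.

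Other inferences are also too strong:
- That every window day is a forced negative, or that dropping the whole window costs no positive days. Up to H days at its end can precede a valid new event.
- That coefficients would reverse sign. The calculations show attenuation, not reversal.
- That the PPV loss is a property of this study. It depends on assumed inputs, and letting the signal stay high during attacks builds in part of the result.

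It is also fair that the section 3 table lists the algorithm as exploratory, that section 2.1 leaves clinical utility to future trials, and that item 1 offers its models and features as examples. However, section 1.1 lists exacerbation prediction as a secondary objective and section 9.1 makes it the first secondary hypothesis. Finally, removing these days from evaluation describes a selected set of days, which is why an all-days sensitivity analysis is needed.

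**Conclusion.** The concern holds as an undefined risk set. Sections 8.1.2.3, 9.4.2 and 9.4.3 together leave most in-episode and relapse-window days in the model as No on a literal reading. The day count rests on the plan's own definitions, apart from the 10-day course and the convention that steroids start on day 0. The effect on slope and PPV is conditional: material with a 2 SD signal, small with a 1 SD signal. AUROC changes little in most scenarios, so the discrimination measure named in section 9.2 is a poor alarm for this problem. The documents do not support a claim that the plan states the mislabelling, or that the harm has a known size.

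**What to change.** Add to section 9.4.3 item 1:

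> For each horizon, patient-days from the start date of an exacerbation until a new event can count under 8.1.2.3 are not at risk. They are excluded from training and from the primary evaluation of the 24-, 48- and 72-hour models, except days at the end of the window from which a valid new event can fall within the horizon. They are treated as not at risk in the recurrent-event model. Relapses are labelled as part of the initial episode, and their days stay not at risk. A sensitivity analysis keeps all days.

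The exception is worded by whether the horizon reaches past the window, not by whether an event followed, so rows are not selected on their outcome.

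The cost is a short paragraph and a date filter. Start and end dates are already required by 8.1.2.3, and its relapse rule already needs the onset date of new symptoms. Analysis follows data collection (9.4.1), so no visit or procedure changes. At most about L+6 patient-days per event leave the main analysis (9 for a 3-day burst, 16 for a 10-day course). Reported performance then describes patients not currently in an episode; the sensitivity analysis shows how far that matters.
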